Number of Events Prior to termination of accrual and evaluation of dose	>2
Evaluation	Assessment of treating physician, daily follow-ups with members of the radiation oncology department with toxicity specific management, documentation of care and progress.
Time to re-initiate Radiation	Once a grade 4 toxicity has resolved and at the discretion of treating radiation oncologist, the patient will be taken off study and treated to a lower dose per fraction. The physician will then close the study.
Action	Closure of trial

- vi. The treating radiation oncologist will hold any radiation treatments as they feel is necessary due to the acute grade 3 or higher toxicity and the timing of re-initiation will be determined by the treating radiation oncologist, but will generally be when the grade 3 or higher toxicity resolves.
- vii. Post-operative wound complications (not acute during radiation, as defined on Appendix III (Radiation dermatitis) are listed.
- viii. If there are any grade 5 post-operative wound complications (Appendix III), then accrual will be halted and the protocol will be reviewed.

I. Documentation Requirements

- i. Treatment interruptions should be avoided when possible by preventative medical measures and nutritional and psychological counseling. Treatment breaks and reasons need to be clearly documented.

J. Compliance Criteria

- i. Section 6 describes appropriate conduct for treatment planning dosimetry. Criteria for both major and minor deviations are provided in Section 6.7.

K. Drug Therapy

- i. Chemotherapy will be delivered prior to radiation at the discretion of the medical oncologists. Prior to radiation, patients will have a repeat MRI scan. Chemotherapeutic regimens will be determined at the discretion of the medical oncologist.

- ii. There are no concomitant medications excluded for this patient population, with exception to chemotherapy. No chemotherapy will be delivered during this course of radiation therapy.

L. Surgery

- i. Patients will have surgical resection 4 to 8 weeks after completion of radiation therapy. Prior to surgery patients will have repeat MRI scan with DCE and DWI sequences. (this is standard practice at our institution and would be done for patients not on protocol).

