- ii. Surgery type will be at discretion of surgeon. Pathology will evaluate the resected specimen and calculate the percent of necrotic (non-viable) tumor in the specimen. This is standard practice at most institutions is done for patients not on protocol. Pathology slides will be sent to the Wisconsin Diagnostic Laboratories ([name]). The designated pathologist reading the slides will be [name]
- iii. The patient's tissue will be stored at the MCW tissue bank. The patients will be consented for this prior to storing tissue.

M. Other Therapy

- i. Supportive Therapy
 - 1. All supportive therapy for optimal medical care will be given during the study period at the discretion of the attending physician(s).

VII. Post-Radiation and Surgery Follow-ups and Patient Assessments (Table 4)

- A. Surgery will be scheduled 4-8 weeks after completion of hypofractionation radiation therapy. After surgery, patients will be seen by the radiation oncologists or surgeons every 4 months (+/- 2 month) for years 1 and 2 from the end of surgery. The exact assessments for these follow-up appointments are listed in Table 3. A 2-year follow-up is standard in STS and then endpoints assessed are overall and disease-free survival, as well as local control, toxicity and QOL in sarcoma studies.
- B. Patients will be evaluated by a surgeon within 2 weeks (\pm 2 weeks) after surgery for evaluation of wound healing (this is standard practice).
- C. Patients will be seen 4 months (+/- 2 month) after surgery (with physical exam) and at this time repeat imaging with a CT chest and MRI of the extremity will be obtained (this is standard practice for patients not on protocol). Treatment after failure will be at the treating team's discretion and documented.
- D. Patient will be seen subsequently 4 months (+/- 2 months) afterwards with repeat imaging with a CT chest and MRI of the extremity for years 1 and 2. Anchor time points are from the end of surgery
- E. Quality of life forms (see Appendix IV) will be filled out pre-treatment and at each follow-up visit beginning at the 4 months (+/- 2 month) from surgery visit with imaging.
- F. Toxicity at all-time points will be assessed using the CTCAE version 4.0. This is the standard toxicity scoring system used in many protocols. QOL assessments will be made using the FACT-L questionnaire (Appendix IV).

Schedule of Events

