Assessments	Within 16 weeks of Registration	Prior to start of RT	During RT	Prior to Surgery (within 4 weeks of surgery)	Surgery	Surgery Follow-up (Within 4 weeks after surgery)	At 4 months (+/- 2 months) after Surgery and every 4 months (+/- 2 months) years 1 and 2
History/physical	X						X

Karnofsky PS	X			X			X
CBC with differential	X						
MRI - tumor site	X			X			X
CT Chest or PET CT	X			X			X
Pregnancy Test (if applicable)	X*						
Toxicity Evaluation		X	X	X		X	X
MSTS, FACT-L	X			X			X
Tissue Collection for Analysis	X				X		
Blood specimen for analysis	X						

Table 4: Study Parameters

*If applicable within 72 hours prior to CT simulation.

VIII. **Tissue/Specimen Submission**

- A. We will collect pretreatment diagnostic tissue and surgical specimens (1 formalin fixed paraffin embedded (FFPE) block) from patients who undergo biopsies to determine diagnosis for this research project, which is standard of care. Biopsy tissue will be sent for outside testing for RNA sequencing. The tissue will be stored on campus. The parameters to be reviewed are histologic, cell kinetic/proliferation, angiogenesis, and molecular markers have been and are under investigation. A number of biomarkers are under investigation by the Sarcoma group. These include SPARC, TYMS, RRM1, ENT1, ERCC1, TOP1, and TOP2A. These biomarkers will be assessed on biopsy and resection specimens for patients enrolled on the study. This assessment will be done in an ancillary study.
- B. Blood specimen (10 ml EDTA) will be collected at the time of lab draw (within 16 weeks of registration) for biomarker testing. Specimens will be stored on campus and sent out for cytokine analysis.

i. Process:

1. After collection, invert tube(s) multiple times to ensure adequate mixing of EDTA.
2. Centrifuge specimen(s) within one hour of collection in a standard clinical centrifuge at ~2500 RPM for 10 minutes at 4°C (preferred). If unable to process samples at 4°C then spinning at room temperature is acceptable if done within 2 hours of draw. If the interval between specimen collection and processing is anticipated to be more than one hour, keep specimen on ice until centrifuging is performed.
3. Carefully pipette and aliquot 0.5 ml plasma into as many cryovials as are necessary for the plasma collected (5 to 8) labeled with and case numbers, collection date/time, time point collected and clearly mark specimen as "plasma". Avoid pipetting up the buffy coat layer.

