 - i. Greater than 2 patients who have any grade 4 or higher toxicity during radiation. If a patient has a grade 4 or higher toxicity, then they will be taken off the study, administered a lower dose per fraction per the treating physician, and the study will be closed. We do expect grade 3 skin toxicity (moist desquamation in areas other than skin folds), as many patients have tumors that extend to the surface of the skin and thus will need to be bloused to get the appropriate dose to these areas. Thus, moist desquamation often occurs.
 - ii. ≥60% of patients with post-operative wound complications.
 - iii. As mentioned above, patients may also withdraw at any point if they wish to not be on study.
- C. The research coordinator and PI will be notified of the withdrawal of a patient and the appropriate documentation will be made.
 - i. The IRB will be notified at the time of withdrawal.
- D. Subjects will not be replaced.
- E. Follow up and data collection for withdrawn subjects will terminate at the time of withdrawal.
- F. Dose Modification
 - i. If any grade 4 toxicity occurs, the dose will be modified based on the BED calculator above and the study will be closed.

XI. **Endpoint Assessment**

- A. Study Design:
 - i. This is a non-randomized Phase II pilot protocol to determine the feasibility, toxicity, and disease control (local control, overall and progression-free survival) using hypofractionated pre-operative radiation therapy in patients with primary localized STS.
- B. Primary Endpoint:

- i. The primary aim of this study is to assess local control. We expect local recurrence rates of <7%. Local and regional recurrence will be defined for each lesion per the treating physician(s). Local recurrence will be defined if the patient has evidence of disease on imaging (MRI or CT or PET CT) or physical exam.

C. Secondary Endpoint:

- i. The secondary objective of this study is to assess quality of life, toxicity (see iii), disease-free survival and overall survival. Disease-free survival is defined as the time from enrollment until documented disease-recurrence or death, whichever occurs first. Patients who are disease-free and alive at the time of analysis will be censored at the time of their last follow-up. Patients will be followed for disease-free survival for a minimum of 2 years.
- ii. Quality of life will be assessed via the FACT-L forms and given at the specified time points above.

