- iii. Toxicity from pre-operative hypofractionated radiation therapy for STS. Based on historical data, we expect there will be minimal toxicity, both acute and long-term. Adverse event rates will be compared at specific times using the CTCAE v 4.0.
- iv. Changes in imaging with MRI (T2, T1 post contrast, DCE and DWI) as well as pathologic correlation (percent necrosis, fibrosis, viable cells and tumor biomarker expression will also be ascertained in this study.
- v. Measure cytokine and tumor gene expression and immune response to radiation therapy and correlate with pathologic and clinical response.

D. Endpoint Analysis:

- i. Crude rates of locoregional recurrences will be documented as well as the time to development of recurrence or relapse. Time of last follow-up or death will also be noted. This will allow us to calculate disease-free and overall survival rates. We will compare these results to an IRB approved database that exists on pre-operative radiation therapy using standard dose and fractionation at 2 Gy per fraction to 50 Gy.
 - 1. This IRB approved database is a retrospective database in which patients with Stage I-III STS of the extremity and superficial trunk were treated with pre-operative radiation therapy using conventional fractionation. Crude rates of locoregional control, disease-free and overall survival will be assessed in this dataset.
 - 2. The data in this database is acquired from all patients who were treated with preoperative RT for localized STS from 2000-2012. This is a retrospective database of the patients treated at Froedtert and the Medical College of Wisconsin
 - 3. The variables included in this database include age, KPS, gender, cardiovascular history, smoking history, disease histology, location of disease, grade, MRI measurements, RT dose and dates, dates of surgery, pathologic findings including size, %necrosis, fibrosis and viable cells, margin status, wound complications, local recurrence, distant recurrence, survival, date of consult and last follow-up, and disease status.

XII. Statistical Considerations

- A. The PRIMARY ENDPOINT of this study is to assess local control
- B. The SECONDARY ENDPOINTS are to assess toxicity, quality of life, disease-free survival and overall survival. Also, changes in imaging (MRI) and pathologic outcomes (biomarkers, percent necrosis, fibrosis and viable cells) will also be assessed.

XIII. Power Considerations for Local Recurrence (Primary Endpoints)

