- A. The primary aim of a 2-year local recurrence rate of less than 3% will be evaluated by a one-sided equivalence test with an equivalence limit of 5% and a type I error rate of 10%. The study will conclude equivalence if the 2-year cumulative incidence of recurrence is less than 12% at the 0.10 type I error level. Power calculations are based on exact binomial probability calculations with an equivalence determined by no more than 12% local recurrence rate (within 5% of 7%), assuming a true 2-year local recurrence rate of 2.5%.
- B. If the true local recurrence rate is 12%, then with 35 patients the probability of observing a recurrence rate of 3.1% or less (≤ 1 of 35) is 8.97% (one-sided type I error = 0.0897).
- C. If the true local recurrence rate is 2.5%, then with 35 patients the probability of observing recurrence of 3.1% or less (≤ 1 out of 35) is 81.0% (Power).
- D. This is as close as we can get to a one-sided equivalence test with 10% type I error and 80% power with exact binomial calculations. The probability of falsely rejecting the null hypothesis (*hypofractionation treatment is worse than standard*) with only 0 or 1 recurrence out of 35 patients is less than 10% if the actual recurrence rate is 12% or more. There will be at least 80% power to reject this hypothesis if the true recurrence is 2.5% or less.

XIV. Considerations for Toxicity, QOL, Disease-Free Survival and Overall Survival (Secondary Endpoints)

- A. Overall survival and disease-free survival will be estimated using the product limit estimator and presented as Kaplan-Meier plots. Cumulative incidence rates will be calculated for local recurrence and adverse events. Quality of life data will be summarized for each time point, and compared using non-parametric statistical methods.
- B. Toxicity will be measured via the CTCAE v. 4.0 and the MSTS score. We will compare toxicity to the standard historical control for preoperative radiation therapy in STS (NCIC, O'Sullivan et. al) (5)
- C. Quality of Life will be measured with the FACT-L validated questionnaire.

XV. References

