Appendix IV-Fact-L (Version 4) Quality of Life

Below is a list of statements that other people with your illness have said are important. **Please circle or mark one number per line to indicate your response as it applies to the past 7 days.**

Below is a list of statements that other people with your illness have said are important. **Please circle or mark one number per line to indicate your response as it applies to the past 7 days.**

PHYSICAL WELL-BEING		Not at all	A little bit	Some- what	Quite a bit	Very much
GP1	I have a lack of energy	0	1	2	3	4
GP2	I have nausea	0	1	2	3	4
GP3	Because of my physical condition, I have trouble meeting the needs of my family	0	1	2	3	4
GP4	I have pain	0	1	2	3	4
GP5	I am bothered by side effects of treatment	0	1	2	3	4
GP6	I feel ill	0	1	2	3	4
GP7	I am forced to spend time in bed	0	1	2	3	4
SOCIAL/FAMILY WELL-BEING		Not at all	A little bit	Some- what	Quite a bit	Very much
GS1	I feel close to my friends	0	1	2	3	4
GS2	I get emotional support from my family	0	1	2	3	4
GS3	I get support from my friends	0	1	2	3	4
GS4	My family has accepted my illness	0	1	2	3	4
GS5	I am satisfied with family communication about my illness	0	1	2	3	4
GS6	I feel close to my partner (or the person who is my main support)	0	1	2	3	4

Q1

Regardless of your current level of sexual activity, please answer the following question. If you prefer not to answer it, please mark this box and go to the next section.

GS7

I am satisfied with my sex life 0 1 2 3 4

Please circle or mark one number per line to indicate your response as it applies to the past 7 days.

EMOTIONAL WELL-BEING

	Not at all	A little bit	Some- what	Quite a bit	Very much
--	---------------	-----------------	---------------	----------------	--------------

GE1
GE2
GE3
GE4
GE5
GE6

I feel sad	0	1	2	3	4
I am satisfied with how I am coping with my illness	0	1	2	3	4
I am losing hope in the fight against my illness	0	1	2	3	4
I feel nervous	0	1	2	3	4
I worry about dying	0	1	2	3	4
I worry that my condition will get worse	0	1	2	3	4

FUNCTIONAL WELL-BEING

	Not at all	A little bit	Some- what	Quite a bit	Very much
--	---------------	-----------------	---------------	----------------	--------------

GF1
GF2
GF3
GF4
GF5
GF6
GF7

I am able to work (include work at home)	0	1	2	3	4
My work (include work at home) is fulfilling	0	1	2	3	4
I am able to enjoy life	0	1	2	3	4
I have accepted my illness	0	1	2	3	4
I am sleeping well	0	1	2	3	4
I am enjoying the things I usually do for fun	0	1	2	3	4

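### Does the pre-surgery FACT-L form that section VII.E leaves out make the quality-of-life endpoint unclear?

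*Combined protocol and SAP*

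**What the plan says.** Section XI.C.ii names the instrument and refers back for timing: "Quality of life will be assessed via the FACT-L forms and given at the specified time points above". It has no list of visits of its own.

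Two earlier places give visits:

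- Section VII.E says the forms "will be filled out pre-treatment and at each follow-up visit beginning at the 4 months (+/- 2 month) from surgery visit with imaging".
- Table 4 has one row for MSTS and FACT-L together. It is marked in three columns: the registration window, the column headed "Prior to Surgery (within 4 weeks of surgery)", and the four-monthly follow-up visits.

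Section VI.L.i sets the interval to surgery: "Patients will have surgical resection 4 to 8 weeks after completion of radiation therapy".

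On analysis, section XIV.A says: "Quality of life data will be summarized for each time point, and compared using non-parametric statistical methods". Section XIV.C adds: "Quality of Life will be measured with the FACT-L validated questionnaire". Neither names a score or a pair of time points. Section XI.D.i.3 lists what the retrospective comparison database holds, starting "The variables included in this database include age, KPS, gender, cardiovascular history, smoking history, disease histology"; the full list has no quality-of-life measure.

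In the Appendix IV form, the sexual-satisfaction item may be skipped ("If you prefer not to answer it, please mark this box and go to the next section"), and the smoking-regret item follows a question on whether the patient ever smoked. The abbreviation list expands the L in FACT-L as General.

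**The concern.** An endpoint defined only by a pointer is as clear as the place it points to, and here there are two places that differ. Read strictly, section VII.E puts the first post-baseline form after surgery, while Table 4 asks for one before it.

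The visit in question is not arbitrary. The treatment under study is pre-operative radiation, and the pre-surgery form is the only FACT-L completed between radiation and resection. If it is not collected it cannot be recovered. If some staff used section VII.E and others Table 4, that time point would exist for only part of the 35 patients.

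The database has no quality-of-life variable, so the comparison in section XIV.A can only be within patients over time, and that depends on which time points exist. The unnamed score adds to the doubt: the whole form, the general items or the separate sections could each be analysed, and the form itself allows items to be left blank.

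**Working it through.** The plan gives no power, effect size or standard deviation for quality of life, so there is no stated figure to reproduce. The check is a count of forms, a timing calculation, and a reading of the passages side by side.

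**Forms per patient.** Follow-up is every 4 months in years 1 and 2 after surgery (sections VII.A and VII.D), nominally months 4, 8, 12, 16, 20 and 24, which is 6 visits.

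| Source | Pre-treatment | Pre-surgery | Follow-up | Total | 35 patients |
|---|---|---|---|---|---|
| VII.E | 1 | 0 | 6 | 7 | 35 × 7 = 245 |
| Table 4 | 1 | 1 | 6 | 8 | 35 × 8 = 280 |

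The difference is 280 − 245 = 35 forms, and 35/280 = 12.5%. It is one form per patient at one visit. The totals assume that every patient completes two years.

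**First form after radiation.** Surgery is 4 to 8 weeks after radiation.

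- Table 4, form within 4 weeks before surgery: earliest 4 − 4 = 0 weeks, latest 8 − 0 = 8 weeks after radiation.
- VII.E, first form 4 ± 2 months (2 to 6 months) after surgery, at 4.348 weeks per month: earliest 4 + 2 × 4.348 = 12.7 weeks, latest 8 + 6 × 4.348 = 34.1 weeks after radiation.

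These are the extremes of the windows. They show what the pre-surgery form adds, not a bias in any estimate.

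**Does VII.E forbid the pre-surgery form?**

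1. Its starting point of four months qualifies the follow-up visits. An earlier post-operative visit exists: the wound check in section VII.B, which Table 4 places within 4 weeks after surgery. Table 4 leaves FACT-L blank there. So the qualifier does a job that agrees with Table 4, namely excluding the wound check.
2. Nothing in VII.E says that no other forms are given. It omits the pre-surgery visit without ruling it out.

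**Which list would staff use?**

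1. The heading of section VII refers to Table 4, and section VII.A sends the reader to a table for the exact follow-up assessments. It calls that table Table 3, but Table 3 holds the radiation compliance criteria, so the number is a slip.
2. MSTS is a planned measure (section III.B.ii.3 and section XIV.B), yet no prose section says when it is done. Its timing appears only in Table 4, in the FACT-L row.
3. Pre-surgery Karnofsky status is also scheduled only in Table 4, and its marks fall in the same three columns.

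A coordinator cannot collect MSTS without reading the row that also calls for FACT-L before surgery.

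**Does any analysis need that form?** Section III.B.ii.1 says only that quality of life is assessed with FACT-L. Sections XI.C, XII.B and XIV add no contrast between radiation and surgery. The time points on which both places agree, baseline and six follow-up visits, support the summary and comparison in section XIV.A.

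**Score.** The form has 7 + 7 + 6 + 7 = 27 general items and 9 added items, 36 in all. The added items are 9/36 = 25%, and the five on breathing, cough, chest tightness and smoking regret are 5/36 = 13.9%. These shares show that the choice of score is a real one. The documents give no way to say how much it would move a result.

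**The case for a change.** The strongest case for a change is that the possible loss is permanent and the remedy is a line of text. The pre-surgery form alone can describe quality of life after radiation without surgery, which is of obvious interest in a trial of pre-operative radiation. No sentence says that Table 4 prevails over section VII.E, and the pointer in section VII.A covers only visits after surgery, so the conflict is not formally settled. Choosing the score and contrasts before seeing the data is also good practice when the form allows blanks.

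Part of this stands. The two places do differ, and section VII.E would read better with the extra visit. If a site used section VII.E alone, that form would be lost.

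The rest is weaker. Nothing in the documents suggests that section VII.E is used in place of Table 4, and the shared MSTS row makes it unlikely. Describing quality of life after radiation alone would be a useful extra, but the plan does not promise it. On scoring, the plan names a validated questionnaire. An analyst would take the scoring and missing-item rule from that instrument's own instructions (an assumption, since the documents do not reproduce them) and use a paired non-parametric test against baseline. Reporting the 27 general items separately is a preference: four of the nine added items (weight, clear thinking, hair loss, appetite) are not specific to the chest.

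**Conclusion.** The concern does not call for a change. The discrepancy is real but amounts to one form per patient, at most 35 forms, at a visit that Table 4 already schedules. Section VII.E is best read as incomplete prose beside a complete table. Aligning it would tidy the wording without a shown effect on any result.

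The unnamed score, contrast, test and missing-item rule are detail that an analyst can supply for a descriptive, unpowered secondary endpoint in a 35-patient pilot. The expansion of FACT-L in the abbreviation list is clerical, since Appendix IV shows which form is used. The primary endpoint, sample size and stopping rules do not depend on any of this.

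The conclusion rests on two assumptions: that staff work from Table 4, as they must for MSTS, and that no claim about quality of life between radiation and surgery is intended, since none is stated.

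### The database comparison in XI.D rests on crude rates, with no time point, origin or estimator shared by the two cohorts

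*Combined protocol and SAP*

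**What the plan says.** XI.D.i covers the trial side first: "Crude rates of locoregional recurrences will be documented as well as the time to development of recurrence or relapse". It adds that last follow-up or death will be noted, so that DFS and OS can be calculated. It then states the comparison: "We will compare these results to an IRB approved database that exists on pre-operative radiation therapy using standard dose and fractionation".

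XI.D.i.1 gives the summary for the database: "Crude rates of locoregional control, disease-free and overall survival will be assessed in this dataset". XI.D.i.2 gives the period: "The data in this database is acquired from all patients who were treated with preoperative RT for localized STS from 2000-2012". XI.D.i.3 lists the variables. Among the dates and outcomes are "RT dose and dates, dates of surgery" and "local recurrence, distant recurrence, survival, date of consult and last follow-up, and disease status". No enrollment date is listed, and recurrence is listed without a date.

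The time-to-event rules stand elsewhere and are written for the trial:

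- XI.C.i starts DFS at enrollment, censors at last follow-up, and promises at least 2 years of follow-up.
- XIII.A sets the primary test on 2-year cumulative incidence of local recurrence against a fixed 12%.
- XIV.A uses the product-limit estimator for OS and DFS and cumulative incidence for local recurrence.
- VII.A plans visits over two years, and VII.D anchors them to the end of surgery.

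None of these sections mentions the database.

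**The concern.** A crude rate is the number of events divided by the number of patients, whatever each patient's time under observation. It rises with follow-up and falls with loss. The two cohorts may well differ on both. The trial guarantees two years, and X.E ends data collection at withdrawal. The database holds patients treated between 2000 and 2012, with follow-up and loss unstated.

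The hypothesis in III.A is that local control and toxicity will be similar to conventional fractionation. XI.D is the only planned disease-control comparison with individual patients who received it. If it is run as written, an apparent difference or similarity may reflect follow-up rather than treatment, and a reader could not correct for this afterwards. Leaving the time point open also allows it to be chosen after the data are seen.

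**Working it through.** XI.D states no number, so there is no figure to reproduce. The check asks how far two crude rates can differ when the treatments are identical.

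**Inputs from the documents** (Introduction, preoperative arm of the cited randomized trial, 5 years): local control 93%, overall survival 73%.

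**Assumptions, not in the documents:** the same disease course in both cohorts; constant hazards; death competing with local recurrence; constant loss per year *c*; trial follow-up of 2-4 years; database follow-up of 5-8 years.

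**Hazards per year.** Local recurrence: h = -ln(0.93)/5 = 0.01451. Death: d = -ln(0.73)/5 = 0.06294.

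**Formula.** With s = h + d + c, the expected crude proportion after potential follow-up T is (h/s) × (1 - exp(-sT)).

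**Equal loss, c = 0.1 in both cohorts.** s = 0.1775 and h/s = 0.0818.

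| Cohort | T (years) | Crude local recurrence |
|---|---|---|
| Trial | 2 | 2.44% |
| Trial | 3 | 3.38% |
| Trial | 4 | 4.16% |
| Database | 5 | 4.81% |
| Database | 8 | 6.20% |

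The gap between identical treatments runs from 4.81 - 4.16 = 0.65 points to 6.20 - 2.44 = 3.76 points. One patient in 35 is 2.9 points.

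**Unequal loss.** Keep c = 0.1 in the trial and set c = 0.5 in the database. Then s = 0.5775 and h/s = 0.0251, and the database crude rate is 2.37% at 5 years and 2.49% at 8 years. Against the trial's 2.44-4.16%, the gap is close to zero at 2 years of trial follow-up and reversed at 3-4 years.

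**Hazard shape.** If 80% of the 5-year events fall in the first two years and loss is 0.1, the database crude rate is 5.3-5.8% against a true 2-year rate of 5.0%. The distortion is then below 1 point.

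**Common 2-year estimate.** With c = 0 and T = 2, s = 0.07746 and h/s = 0.1874, which gives 2.7%. Cumulative incidence at 2 years with censoring targets this same value in both cohorts, so the expected gap is zero under these assumptions, provided loss is unrelated to outcome.

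**DFS and OS, only if crude covers the whole list.** The hazard of relapse or death is -ln(0.58)/5 = 0.10895. With no competing event and loss 0.1, crude against crude is 17.8-29.5% (trial) v 33.8-42.3% (database) for relapse or death, and 10.7-18.5% v 21.5-28.1% for death.

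**Precision.** One recurrence in 35 has an exact 95% interval of about 0.1-14.9%. For 2-year DFS near 80.4%, the half-width is 1.96 × √(0.804 × 0.196/35) = 0.132, about 13 points.

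**The case against.** The strongest reply is that most of the missing material is already in the plan. XI.D records time to recurrence and date of last follow-up. XIV.A names the right estimators and does not say that they apply to trial patients only. XI.C's censoring rule could be applied to the database, which lists last follow-up. VII.A says "A 2-year follow-up is standard in STS and then endpoints assessed are overall and disease-free survival". A reader might infer from this point that the plan defines no time point, origin or censoring rule at all. That would be wrong: it defines them for the trial. What remains is that the only text on how the database is to be summarised says crude rates, and that nothing links it to those rules.

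The word crude may also govern locoregional control alone. On that reading the DFS and OS figures above fall away as an estimator problem, although a shared time point and origin are still unstated for them.

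The origin by itself is a small matter. A one-month shift changes 2-year DFS by about 0.10895/12 × 0.804 = 0.007, or 0.7 points. The illustrated gaps in local recurrence are also small beside the sampling error of 35 patients. Both objections stand and limit the weight of the point. Neither justifies keeping a bias that a few lines can remove.

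**Conclusion.** The point holds as a secondary matter worth considering. As written, XI.D can show a difference between identical treatments because crude rates mix risk with follow-up and loss. This is clear for locoregional control and conditional on the reading of crude for DFS and OS.

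The illustrated gap of about 0.7 to 3.8 points in local recurrence rests on assumed follow-up, equal loss and constant hazards. It shrinks with early events and can vanish or reverse with heavier loss in the database.

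Two stronger readings are tempting and not supported. A reader might infer that the comparison favours hypofractionation because the older cohort was probably followed longer. The documents state neither follow-up nor loss for the database, so no direction can be claimed. A reader might also infer that the primary conclusion is compromised. It is not: the rule of at most 1 recurrence in 35 is set against a fixed 12% and does not use the database.

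**What to change.** In XI.D, replace crude rates with the same estimates in both cohorts: 2-year cumulative incidence of local recurrence with death as a competing event, and 2-year Kaplan-Meier DFS and OS. Use one origin recorded in both, for example the start of RT, and censor at last follow-up or 2 years, whichever comes first. Report the length of follow-up and the loss in the database.

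State that this origin serves the database comparison only and that the enrollment-based DFS of XI.C remains the trial's own endpoint. Report how many enrolled patients never started RT, since they drop out of this comparison.

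The cost is a few lines of protocol text, a small re-analysis and a second DFS origin that must be clearly labelled. Recurrence dates may need chart look-up for database patients who relapsed, because the listed variables do not name them. The change removes an avoidable bias but does not make the comparison precise, so the estimates should be given with confidence intervals.
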